
Recruitment and screening procedures are detailed in section 4.b and 4.d of this document, respectively. Informed consent for the study will take place using the following procedures. If a person fully meets eligibility criteria as determined through screening and continues to express interest in enrollment following screening, an informed consent session will take place either immediately or will be scheduled for a future time, depending on the individual's preference/availability. The consent process will take place either remotely through digital consenting available from REDCap or in person. In all cases, informed consent will be obtained only by authorized, trained study personnel affiliated with USC and not by employees of *Activ Sitting, Inc.* to avoid conflict of interest. Each prospective participant will be given time to read the consent and discuss their options with project staff and family members. To ensure ample time to peruse the consent information, we routinely mail or e-mail copies of a sample informed consent document to each interested party. When the prospective participant is ready, a dialogue regarding the study will ensue. The study team member is responsible for guiding the discussion, and will be instructed to follow a standard format to ensure all required elements are introduced. Explanations will cover all aspects of participation requirements, participants' rights, and other relevant information. Individuals will have an opportunity to ask questions about the study and, if they choose to enroll, will sign a consent form. They will be provided with a copy of the consent form.

Study Procedures: General

This study includes three stages: (1) Focus Group, (2) In-lab Testing, (3) In-home Testing. Study procedures for only the in-home testing phase are delineated below for purposes of clinicaltrials.gov.

Study Procedures: In-home Testing Stage

Overview. A separate set of users ($N=15$) who did not participate in the in-lab activities will complete an in-home trial of a *FitSitt* prototype. The trial period will last between 3 and 7 days (depending on availability of prototypes and scheduling) and will capture free-living feasibility, acceptability, and potential health-relevant short-term benefits of the system. Participation will require two in-person contacts within approximately a 2-week period, which will include pre-session activities, an in-home orientation to *FitSitt*, and a follow-up visit in-home.

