 - Screening, Contact, Referral Form: The screening form includes details for each of the three stages of the study (i.e., focus group, in-lab, in-home) and will be asked based on which stage we are recruiting for at the time. Questions are based on inclusion and exclusion criteria for each study stage. Additionally, important demographic details will be asked (i.e., age, sex, race/ethnicity, TV watching time) for purposes of recruiting a diverse sample of participants as required by the funding sponsors. This screening will be administered as a smart form such that select questions will only arise based on individuals' responses to previous questions and stages of study recruitment. The form includes a section for participant contact information as well as referral source.
 - Background Questionnaire: Basic *demographic*, health-related, health behavior, and technology use data will be gathered using a study-specific questionnaire to characterize the sample. This questionnaire will be administered as a smart form such that questions will branch to additional questions based on responses from the individual. The form is expected to take approximately 5 minutes to complete.
 - Initial Impressions of FitSitt: *Feasibility* and *acceptability* of *FitSitt* will be assessed using a study-specific questionnaire targeting users' cursory impressions of the system. Users are asked a variety of questions targeting issues ranging from perceived ability of the system to meet their health needs to the likelihood the system could be integrated into their daily lives. The form is expected to take approximately 3 minutes to complete.
 - Self-Efficacy for Using FitSitt scale: *FitSitt use self-efficacy* will be assessed using a study-specific adaptation of the Self-Efficacy for Exercise scale (Resnick & Jenkins, 2000). Items have been modified to focus on using *FitSitt* as the mode of SA disruption rather than addressing exercise in general terms. The form is expected to take approximately 3 minutes to complete.
 - Activity Monitor Log: This log was created to assist the research team in data analysis and interpretation of data collected from the activPAL/ActiGraph activity monitors. On this

form the user will document any instances of when the monitors fell or were taken off, wake/bed times, and any other comments they would like to include about monitor wear.

5.b.ii. Qualitative Instruments

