In-home testing data related to activity, physiological parameters, and *FitSitt* usage patterns will only include activity that takes place during waking hours, as determined by ActivPAL's (and/or ActiGraph's) proprietary algorithm and corroborated by participant activity monitor logs. We will capture and report descriptive statistics on factors such as: *sitting/lying behavior* (total duration sitting/lying per day, mean duration of individual sitting/lying bouts over the day, number of sitting/lying bouts per day, number of sit-to-stand transitions per day), and *activity level* (total sedentary time [ActivPAL/ActiGraph proprietary algorithm], total step counts per day, total stepping time per day). Objective *FitSitt* usage data will be aggregated to produce meaningful summaries of chair usage, such as: *seat occupancy* (total duration sitting in *FitSitt* per day, duration of *FitSitt* sitting bouts per day), *treadle usage* (duration of pedaling bouts per day, frequency of pedaling bouts per day, total time pedaling per day, mean speed during daily pedaling bouts), *synchro-tilt/recline usage* (number of times recliner is engaged per day, mean duration of recliner engagement per day). Additionally, *pain, fatigue, stiffness, and physical activity/sedentary activity behaviors* (self-reported and objective) will be collected both pre-use of the system and at the conclusion of the study. Pre-post scores will be compared, for exploratory purposes, using a paired samples *t*-test (or Wilcoxon signed-rank test) to indicate changes, if any, after having *FitSitt* in the home for a short time. Additionally, we will explore the association of *FitSitt* adherence (minutes of treadle usage dichotomized at the median) to confidence to use *FitSitt* using Spearman correlation. Normalizing transformations will be applied to variables as appropriate; sparse data may be recoded to dichotomous or ordinal data.

Power Analysis

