The purpose of this study is to continue *FitSitt* development, and to test the feasibility of study procedures that would be used in a larger study investigating the efficacy of the system to decrease sedentariness in older adults. Accordingly, power calculations are not appropriate. However, sample sizes chosen for each stage of testing are justifiable based on previous research. Iterative product development requires only small samples—5 to 20 users per prototype iteration (Faulkner, 2003)—justifying our modest sample sizes of $N=15-30$. The additional participants beyond the high end of the recommended range will increase chances of identifying lower-level usability issues (Faulkner, 2003; Virzi, 1992). The data from this pilot study will elicit rich information for a properly powered, more in-depth study in Phase II.

References

Atlas, S. J., & Deyo, R. A. (2001). Evaluating and managing acute low back pain in the primary care setting. *Journal of General Internal Medicine*, 16(2), 120-131.

Beck, K. L., Weeks, L. E., Montelpare, W. J., & MacDonald, D. J. (2016). Identifying important factors for older adults' physical activity participation across individual/group, structured/unstructured contexts. *European Journal of Ageing*, 13(3), 209-218. <https://doi.org/10.1007/s10433-016-0376-1>

Berk, D. R., Hubert, H. B., & Fries, J. F. (2006). Associations of changes in exercise level with subsequent disability among seniors: A 16-year longitudinal study. *The Journals of Gerontology Series A: Biological Sciences and Medical Sciences*, 61(1), 97-102. <http://www.ncbi.nlm.nih.gov/pubmed/16456200>

Bertheussen, G. F., Romundstad, P. R., Landmark, T., Kaasa, S., Dale, O., & Helbostad, J. L. (2011). Associations between physical activity and physical and mental health--a HUNT 3 study. *Medicine & Science in Sports & Exercise*, 43(7), 1220-1228. <https://doi.org/10.1249/MSS.0b013e318206c66e>

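### Splitting treadle minutes at the median before a Spearman correlation discards about a quarter of the information at N=15, gives no reason, and leaves the median participant's group undefined

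*Combined protocol and SAP*

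**What the plan says.** Section 5.c sets out an exploratory association between FitSitt adherence and confidence to use FitSitt, measured by Spearman correlation. Adherence is defined as "minutes of treadle usage dichotomized at the median". The split is unconditional. No reason is given, and there is no rule for a value equal to the median.

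Four other places bear on this:

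- **Sensor summaries (5.c).** Treadle use is already summarised by day, including "total time pedaling per day" and "mean speed during daily pedaling bouts".
- **Recoding (5.c).** The only other text on dichotomizing is that "sparse data may be recoded to dichotomous or ordinal data". It is a general option and is not tied to treadle minutes.
- **Confidence (5.b.i).** Self-efficacy for using FitSitt "will be assessed using a study-specific adaptation of the Self-Efficacy for Exercise scale". This multi-item scale appears to be the confidence variable.
- **Sample and exposure (5.a.i, in-home Overview).** There are 15 in-home participants, and each keeps the chair for 3 to 7 days.

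The Power Analysis section says that "power calculations are not appropriate".

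**The concern.** A cut is sometimes made to avoid skew or outliers. Spearman correlation deals with both by ranking, so the cut brings no benefit here. It replaces 15 ordered values with two groups and treats a participant just above the median the same as the heaviest user.

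Two things follow. The coefficient is pulled toward zero, has a ceiling below 1, and is less likely to show a real monotone association. And because 15 is odd, one participant sits exactly on the cut, so the result depends on a rule that the plan does not state.

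The stake is modest. The pilot is meant to inform a larger Phase II study, and a needlessly shrunken coefficient is a poorer input to that. No decision in this study depends on it.

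**Working it through.** The plan gives no effect size, test level or power for this analysis, so there is no figure of its own to reproduce.

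**Inputs from the documents.** N = 15 (5.a.i); split at the sample median and Spearman correlation (5.c).

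**Assumed for illustration.** Bivariate normality, true correlations of 0.3 to 0.7, two-sided 0.05, no ties unless stated.

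**1. Ceiling and rank information (no distribution assumed).** Let the ranks be 1 to 15, with mean 8. Let S be the sum of confidence ranks in the high group and m the size of that group. The split coefficient is

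r = (S − 8m) / sqrt[(7 × 8/15) × 280] = (S − 8m) / 32.33,

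where 280 is the sum of squares of the ranks about their mean. The largest value occurs when the high group holds the top ranks:

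- 7 high: S = 9 + … + 15 = 84, so r = (84 − 56)/32.33 = 0.866.
- 8 high: S = 8 + … + 15 = 92, so r = (92 − 64)/32.33 = 0.866.

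0.866² = 0.75, so 25% of the rank information is lost under either grouping.

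**2. Simulation at n = 15** (200,000 samples per setting, t-approximation, 7 high and 8 low):

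| True correlation | Mean coefficient, continuous | Mean coefficient, split | Power, continuous | Power, split | Full-rank n with the split's power |
|---|---|---|---|---|---|
| 0.3 | 0.270 | 0.224 | 17.6% | 13.6% | 11.5 |
| 0.4 | 0.362 | 0.301 | 28.5% | 20.9% | 11.3 |
| 0.5 | 0.455 | 0.380 | 43.9% | 31.1% | 11.1 |
| 0.6 | 0.550 | 0.461 | 62.3% | 44.6% | 10.9 |
| 0.7 | 0.647 | 0.545 | 80.6% | 61.1% | 10.7 |

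The coefficient is about 16–17% smaller. In power terms the split costs 15 − 11.5 = 3.5 to 15 − 10.7 = 4.3 participants, or 23% to 29% of 15. Null rejection rates are 5.2% (continuous) and 5.4% (split), so the comparison is fair. Holding both tests at exactly 5% by randomized critical values gives the same picture: 43.0% versus 29.7% at a correlation of 0.5.

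**3. The median participant.** If that person's confidence rank is k, moving them from low to high changes S − 8m by k − 8. The denominator stays at 32.33. The coefficient therefore changes by (k − 8)/32.33, at most 7/32.33 = 0.217. In the simulations the mean absolute change is 0.09 to 0.11, and the p < 0.05 result changes in 10% to 19% of samples.

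**4. Departures from the assumptions.**

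- *Ties in confidence* (40% tied, assumed): power 40% continuous versus 28% split at 0.5.
- *Ties in minutes* (seven lowest tied, assumed): at 0.5, mean coefficient 0.42 versus 0.38, and power 38% versus 31%. The loss is smaller but remains.
- *True step at the median* (1.2 SD, assumed): the split does better, 57% versus 43%.

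**5. Precision either way.** For a continuous coefficient of 0.55, Fisher's z is 0.618 with SE sqrt[(1 + 0.55²/2)/12] = 0.310. The 95% interval is about 0.01 to 0.84.

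**The case against.** The strongest reply is that this barely matters. The analysis is exploratory, the plan declines power calculations, and Aim 2's milestones concern data collation and the failure-modes report, not this correlation. The plan names no significance level, so the power figures and the significance changes describe a test it never specifies. An interval of 0.01 to 0.84 is far wider than a shift from 0.55 to 0.46. The quarter lost assumes untied minutes, while voluntary use could produce clusters of low users. A threshold effect would favour the split. The sparse-data sentence is permissive, so a prespecified split does not contradict it. And the median problem disappears if the number analysed is even and nobody is tied at the cut.

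Much of this stands, and it limits the point to a minor one. The power figures are illustrations. The sparse-data sentence does not forbid the split; it only fails to explain it. But the ceiling of 0.866 and the maximum shift of 0.217 need no test level or distribution beyond untied data, and the loss persists with tied minutes. No passage claims that confidence steps up at the sample median, which depends on who happens to enrol. An exploratory label explains a small sample; it is not a reason to discard part of it.

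**Conclusion.** The concern holds. The split is unnecessary for a rank correlation, no reason is given for it, and it leaves one participant's group undefined when an odd number is analysed. Without ties it discards exactly 25% of the rank information at N = 15. Under assumed bivariate normality it performs like a full-rank analysis of about 11 participants. Tied minutes would reduce the loss, and a true threshold at the median would reverse it. The consequence is small because the result is exploratory and imprecise under either method, but the plan can be improved at almost no cost.

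**What to change.** In section 5.c, replace the bracketed definition of adherence with each participant's mean daily pedaling time over their trial days, kept continuous. Report the Spearman coefficient with a 95% confidence interval. Keep the sparse-data sentence as the only route to dichotomizing. High and low users may still be shown descriptively; if so, state which group takes a value equal to the median.

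The daily basis matches the treadle summaries already listed and keeps the 3-to-7-day difference in trial length out of the measure. The same clause should say how partial installation and retrieval days are handled.

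The cost is one clause. The sensor summary "total time pedaling per day" is already planned, so no new form, visit or data item is needed.
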